7.1. Evaluation/Definition of Primary Outcome

The primary endpoint of the REGARD-VAP trial will be analysed as a binary outcome (i.e. not as a time to event outcome) because dates may reflect timing of observations rather than actual failure. In this analysis, any participant with incomplete follow-up and no event observed to date will be classed as not having experienced an endpoint.

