5.3. Comparison of Losses to Follow-up

The numbers (with percentages) of losses to follow-up (defaulters and withdrawals) over the 60 days of the study follow-up will be reported and compared between the short and long groups with absolute differences (95% CI). Any deaths (and their causes) will be reported separately within the section on SAEs and complications.

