5.4. Description of Available Data

The availability of data for baseline assessments as well as for primary and secondary endpoints will be described for all appropriate trial time points. Data items are defined as available if the case report form has been completed and if the information provided can be used in the analysis. Summaries will be provided overall and by trial arm, and the number of available data items will be presented together with the number of data item expected and a percentage indicating the rate of data compliance for each endpoint and time point (i.e. investigating what percentage of expected data is actually available).

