7.3. Adjustment of P values for Multiple Testing

There is no multiple testing as only a single primary outcome is considered. All additional analyses are undertaken with an intention to further inform the results from the primary analysis. Therefore significance levels used will be 0.05 and 95% confidence intervals will be reported.

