7.4. Missing Data

Minimal amounts of missing data are expected in the REGARD-VAP study as most information could be retrieved from the medical notes and frequent follow-ups from the research teams. Loss to follow-up may arise primarily in cases where participants formally withdraw from all further follow-up or relocate or their medical records can no longer be accessed. Low percentages of missing data are not expected to have a significant impact on the trial results, and therefore no sensitivity analysis to examine the impact of missing data is planned if complete outcome data is available for more than 95% of participants (i.e. less than 5% of participants are lost or withdraw from follow-up before 60 days).

However, in the event that the extent of missing data will exceed this level, multiple imputation models will be used to adjust for missing data. Data will be imputed based on the covariates used in the multivariable models (allowing for a possible non-linear effect of age), the log(last follow-up time) and a treatment failure indicator which will be set to missing for those with incomplete follow-up due to loss / withdrawal. Twenty imputed datasets will be created, and results will be pooled using the standard methodology (Rubin's rule) and 'mice' package in R¹⁰. Visual checks to compare the distribution of observed and imputed values will be performed to ensure the imputation model includes non-linear effects of continuous variables where appropriate. Multiple imputation assumes that the missing data follows a missing at random mechanism, i.e. the probability of an observation being missing can be explained by the observed data. Under this assumption, an imputation model that includes the appropriate variables will produce unbiased results. A secondary sensitivity analysis to assess the potential impact of missing data will also include a data missing not at random scenario, assuming that participants with missing data have worse outcomes than those with complete follow-up data, following the approach by White *et al*¹¹.

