7.7. Sensitivity Analysis

No sensitivity analysis in addition to that discussed in the above sections is planned in the context of the primary analysis. The above-described analyses (including both the ITT and PP analysis, which are parts of the primary analysis described above) are sufficient to assess the robustness of the trial results.

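### SAP 7.1 counts participants lost before an event as event-free in the non-inferiority test, and when less than 5% are lost no planned analysis shows whether the conclusion depends on that coding

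*SAP*

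**What the plan says.** SAP 7.1 makes the primary endpoint binary and adds that "any participant with incomplete follow-up and no event observed to date will be classed as not having experienced an endpoint". Under SAP 7.2 the proportions built this way are compared in the ITT and per-protocol populations, and non-inferiority requires the upper limit of the two-sided 90% interval for the unadjusted difference to be below 12%. Protocol 10.1 also requires the adjusted limits to be below the margin.

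SAP 7.4 handles the same participants differently. It states that "no sensitivity analysis to examine the impact of missing data is planned if complete outcome data is available for more than 95% of participants". If loss is greater, "multiple imputation models will be used to adjust for missing data", from a model that includes the covariates, "the log(last follow-up time) and a treatment failure indicator which will be set to missing for those with incomplete follow-up". The same section then adds a secondary sensitivity analysis under a missing-not-at-random assumption, in which participants with missing data do worse.

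SAP 7.3 says "All additional analyses are undertaken with an intention to further inform the results from the primary analysis", and SAP 7.7 says "No sensitivity analysis in addition to that discussed in the above sections is planned in the context of the primary analysis". SAP 5.3 compares losses between the arms, and SAP 5.4 describes completeness by arm, "investigating what percentage of expected data is actually available".

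The sample size section (Protocol 10.2, SAP 2.5) expects a 55% event rate and loss of up to 10%. Protocol 7.8 says discontinued participants are followed to day 60. It later says such patients are not followed and are replaced. SAP 6 defines ITT as everyone randomised.

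**The concern.** A fixed no-event value is a favourable guess for people whose outcome is unknown, and it enters the estimate that decides the trial. If the short arm is truly worse and loss is equal, the rule shrinks the difference and makes non-inferiority easier to declare. If more are lost from the short arm the pull is stronger. If more are lost from the long arm it works against the short strategy. The documents give no loss by arm, so the direction cannot be known in advance.

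Below the 5% trigger, a reader of the trial report would see how many were lost from each arm but not whether the conclusion survives other assumptions about them. Protocol 7.8 affects how many participants fall under the rule: a randomised participant who is discontinued and not followed stays in ITT and is scored event-free.

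**Working it through.** **The plan's own figures.** A pooled two-proportion calculation for 55% v 67%, one-sided 5%, 80% power, gives per arm [1.645√(2×0.61×0.39) + 0.842√(0.55×0.45 + 0.67×0.33)]² / 0.12² = 203.2. That is 204 per arm or 408 in total, close to the stated 412. The ratio 412/406.5 = 1.014 is plausible as group sequential inflation, but I did not derive that factor. For loss, 412/0.90 = 457.8, consistent with 460. This inflation treats the lost as non-evaluable, whereas SAP 7.1 keeps them in the denominator as non-events.

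**The trigger.** More than 95% of 460 complete means more than 437, so at most 22 lost (22/460 = 4.8%).

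**Effect of the rule.** Let p be an arm's true event rate, f the fraction lost event-free, and r the risk of the lost relative to the arm. The expected observed rate is p(1 − f·r). With equal f and r the observed difference is the true difference times (1 − f·r), so it moves toward zero.

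Assumptions: true rates 67% v 55% (exactly at the margin), 230 per arm, one final analysis, unadjusted ITT, Wald interval, exact binomial enumeration. The documents give neither f by arm nor r, so both are varied. Example at 6% short, 3% long, r = 1: 0.67×0.94 − 0.55×0.97 = 0.6298 − 0.5335 = 0.0963, against a true 0.12.

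Type I error (5.0% with no loss):

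| Loss short / long | r = 1 | r = 0.25 | r = 0.10 |
|---|---|---|---|
| 4% / 4% | 6.4% | 5.3% | 5.1% |
| 10% / 10% | 8.7% | 5.9% | 5.3% |
| 6% / 3% | 13.4% | 6.6% | 5.6% |
| 3% / 6% | 2.8% | 4.4% | 4.7% |

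All rows except 10%/10% lie below the trigger.

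**An example below the trigger.** Suppose 14 short and 7 long are lost (21 of 460), with events 123/230 v 114/230.

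- SAP 7.1: difference 0.5348 − 0.4957 = 0.0391, SE 0.0466, upper limit 0.0391 + 1.645×0.0466 = 0.1157. Passes.
- Lost at a quarter of the observed risk (123/216 = 0.569; 114/223 = 0.511): add 14×0.569×0.25 = 1.99 and 7×0.511×0.25 = 0.89 expected events. The upper limit is 0.1205. Fails.
- Lost at half the observed risk: add 3.99 and 1.79. The upper limit is 0.1252. Fails.
- Lost at the full observed risk, analysed as observed cases only: 123/216 v 114/223, difference 0.0582, SE 0.0475, upper limit 0.1364. Fails.

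The SAP 5.3 table would show a loss difference of 3.0 points (95% CI −0.8 to 6.8), which says nothing about the margin.

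**Last follow-up time.** The documents do not define this variable for participants who die. If follow-up ends at death, then among participants with a known outcome a follow-up time well short of day 60 occurs only with an event. The imputation model could then predict the event almost perfectly from that variable and impute most of the lost as events.

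**Protocol 7.8.** One sentence has discontinued participants, including those never randomised, followed to day 60. Another has them neither followed nor kept, but replaced. The second comes after text on rescreening and may be meant for enrolees never randomised, but it is not limited to them.

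**The case against.** Much of the opposing case stands.

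- A reader might infer that the SAP leaves the rule untested altogether. It does not. Above 5% loss, SAP 7.4 plans both imputation and a missing-not-at-random scenario that assumes worse outcomes for the lost, which directly challenges SAP 7.1. At the planned loss of up to 10% these would run.
- A reader might infer that the rank of the imputation is an open contradiction. The ordinary reading of SAP 7.3, 7.4 and 7.7 is that SAP 7.1 decides and the rest is supportive. What is missing is only a sentence saying so.
- The 55% rate is whole-trial risk. People event-free when lost, especially late, carry less, and at one-tenth of the arm's risk the inflation is slight.
- Non-inferiority needs more than one interval. Assuming 10% random non-adherence, requiring both unadjusted ITT and per-protocol limits to pass gives type I error at full / half / quarter risk of about 4.6 / 4.2 / 3.9% at 4%/4% loss and 10.2 / 6.3 / 4.8% at 6%/3%. So balanced loss below the trigger stays under 5%, while unequal loss may not.
- The 14 v 7 example was chosen near the margin, and at quarter risk it fails by only 0.05 points.

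What remains is that, below 5% loss, the plan contains nothing that would tell a harmless case from a decisive one.

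**Conclusion.** The concern holds as a gap in testing and wording, worth fixing but not fatal. The coding can change the primary conclusion when loss is unequal and the result is close to 12%, and below 5% loss no planned analysis would reveal it. With balanced loss under 5% the effect is small: at most 6.4% against 5.0% for one unadjusted ITT interval. All these sizes rest on assumed loss by arm, assumed residual risk and a single final look. They are upper bounds for the full decision rule.

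Two stronger conclusions are tempting but unsupported. One is that the rule favours the short arm: with more loss in the long arm it is conservative. The other is that the deciding analysis should become an imputation by arm and last weekly event-free contact. SAP 2.7 screens for recurrence only until discharge, and Protocol Appendix B has weekly procedures only in hospital, so weekly composite status after discharge is not clearly collected. The advantage of that method in simulation also rests on loss assumed unrelated to outcome.

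**What to change.** 1. SAP 7.4: remove the 95% trigger. At any level of loss, report the planned imputation, with randomised arm named in the model, and the missing-not-at-random analysis. Extend the latter to a two-arm tipping point that varies the risk of the lost separately by arm and shows where the upper 90% limit crosses 12%.
2. SAP 7.1/7.2: state which analysis decides, and that a non-inferiority conclusion reversed under plausible assumptions about the lost is reported as not robust.
3. SAP 7.4: define last follow-up time for participants who die before it is used in the imputation.
4. Protocol 7.8: reconcile the two sentences with the ITT definition, so that day-60 status is sought for every randomised participant, subject to consent, and randomised participants are not replaced in ITT.

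The cost is SAP wording, one short additional analysis and a protocol clarification. The downside is a little more work and possibly a less favourable supportive result.

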7.2. Statistical Methods Used for Analysis of Primary Outcome

Based on both the ITT and PP population, the proportions of participants experiencing the primary endpoint will be tabulated by treatment group. If the absolute, upper two-sided 90% CIs around the absolute unadjusted difference is less than 12%, then the criteria of non-inferiority will be met.

A multivariable logistic regression model, will be applied on the ITT population to calculate the estimates of the treatment differences adjusted for baseline patient characteristics described above. Categories with low counts may be combined. For example, in the event of comorbidities with very low counts, these comorbidities may be combined to avoid difficulties with the maximum likelihood estimation of the logistic model. Where no

information has been entered on the comorbidities, the participants will be considered not to suffer from these comorbidities.

For the PP population, inverse probability weighting⁹ will be applied to calculate the estimates of the treatment differences using the same baseline patient characteristics as above.

For these multivariate logistic regression models, residual and predicted values produced from the model will be examined to assess the assumptions of the model. Specifically, the assumption of linearity between the predicted log odds and the covariates is assessed by plotting lowess graphs. The independence of the error terms will be considered. Influential cases are investigated by plotting the standardised Pearson's residuals against the predicted probabilities and the leverage of the individual observations.

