10. STATISTICS AND ANALYSIS

10.1. Description of Statistical Methods for Primary and Secondary Outcomes

Descriptive statistics will include frequency tables for categorical data, means (SDs), or medians (interquartile ranges) depending on the distribution of the data. Categorical variables will be compared with χ^2 and Fisher exact tests as appropriate and continuous variables with unpaired, 2-tailed t tests or nonparametric Wilcoxon rank sum tests as appropriate.

The primary and secondary outcomes of the study populations will be analyzed using both unadjusted and adjusted methods in both the per-protocol and intention-to-treat populations. Adjustment will be done with inverse probability weighting, using baseline patient characteristics (study site, age, gender, comorbidities, residence prior to admission, type of ICU admitted to, SOFA score, VAP infection with CRE, maximum heart rate and minimum mean arterial blood pressure on randomisation day, duration of intubation prior to developing VAP, reason for intubation, number of days from first respiratory symptom onset to first day of appropriate antibiotics) as independent variables.

Subgroup analysis will be performed using the primary outcome as the dependent variable amongst patients with VAP caused by Gram-negative non-fermenters and carbapenem-resistant bacilli. VAPs caused by Gram-negative non-fermenters have been previously shown to be associated increased recurrence [10,11]. VAPs caused by carbapenem-resistant bacilli have no standardised treatment. This will be exploratory as the sample sizes for each of this groups will not reach adequate power.

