This is a non-inferiority trial with a hierarchical noninferiority–superiority hypothesis. The first analysis to be conducted will be for determination of non-inferiority. Only if non-inferiority is established by this primary analysis, a second analysis for superiority will be conducted using closed testing methods without requiring adjustment of the significance level for multiple comparisons. [39] The trial estimates for the primary outcome will be calculated with the absolute risk difference (proportion of participants with the primary outcome in the short arm minus that in the long arm). Hence, non-inferiority will be concluded if the upper boundaries of the one-sided 95% confidence intervals from both unadjusted and adjusted analyses are below the non-inferiority margin. The purpose of using both adjusted analyses on the intention-to-treat and per-protocol populations to determine non-inferiority is to minimise the inflation of type 1 error associated with non-adherence in non-inferiority trials. [40] Superiority will be declared if the entire confidence intervals for all the trial estimates are above zero.

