7. ANALYSES TO ADDRESS PRIMARY AIMS

All analyses will be formed with R⁷. All packages used in the analysis will be cited according with the corresponding version numbers. All analysis code will be published in an open access online repository with the final manuscript.

All primary and secondary outcomes of the study populations will be analysed using both unadjusted and adjusted methods in both the PP and ITT populations. The purpose of using both adjusted analyses on the intention-to-treat and per-protocol populations to determine non-inferiority is to minimise the inflation of type 1 error associated with non-adherence in non-inferiority trials⁸.

Multivariable regressions will be performed with inverse probability weighting, using baseline patient characteristics (study site, age, sex, comorbidities, residence prior to admission, type of ICU admitted to, SOFA score, VAP infection with CRE, maximum heart rate and minimum mean arterial blood pressure on randomisation day, duration of intubation prior to developing VAP, reason for intubation, number of days from first respiratory symptom onset to first day of appropriate antibiotics) as independent variables.

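### Protocol 10.1 requires both unadjusted and adjusted limits below 12%; the pass rule in SAP 7.2 names only the unadjusted difference, and SAP 7 contradicts it

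*SAP*

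**What the plan says.** **Protocol 10.1.** The outcomes are to be "analyzed using both unadjusted and adjusted methods in both the per-protocol and intention-to-treat populations". The decision sentence reads "non-inferiority will be concluded if the upper boundaries of the one-sided 95% confidence intervals from both unadjusted and adjusted analyses are below" the margin. The scale is fixed: "The trial estimates for the primary outcome will be calculated with the absolute risk difference". The method of adjustment is also fixed, with no split by population: "Adjustment will be done with inverse probability weighting, using baseline patient characteristics".

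**SAP 7.** It repeats the protocol's explanation that the purpose of "using both adjusted analyses on the intention-to-treat and per-protocol populations to determine non-inferiority is to minimise the inflation of type 1 error", and describes the regressions as inverse probability weighted.

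**SAP 7.2.** It opens "Based on both the ITT and PP population, the proportions of participants experiencing the primary endpoint will be tabulated by treatment group". The pass rule follows: non-inferiority holds if the "upper two-sided 90% CIs around the absolute unadjusted difference is less than 12%, then the criteria of non-inferiority will be met". A logistic model "will be applied on the ITT population to calculate the estimates of the treatment differences adjusted for baseline patient characteristics described above"; weighting is reserved for the PP population. No pass criterion is attached to either adjusted estimate.

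**Elsewhere in the SAP.** Section 7.7 calls the ITT and PP analyses parts of the primary analysis. Section 1 says primary reporting follows the SAP. Section 2.5 gives 412 patients for 80% power at one-sided 5%, a 55% event rate and a 12% margin, and 460 after 10% loss.

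**The concern.** The non-inferiority verdict is the trial's main conclusion and the gateway to the superiority test, so it should follow uniquely from the documents. It does not, for three reasons.

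- **Which estimates must pass.** The protocol names unadjusted and adjusted limits. SAP 7.2 names the unadjusted limit. SAP 7 gives the adjusted analyses a deciding role that 7.2 does not carry through.
- **Which populations must pass.** Both documents analyse ITT and PP, and the text points towards both counting. Neither says that failure in one population defeats the claim.
- **How ITT is adjusted.** It is weighting in Protocol 10.1 and SAP 7, and logistic regression in SAP 7.2. A logistic model gives an odds ratio, and SAP 7.2 does not say how a risk difference and its interval are obtained for comparison with 12%.

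The trial statistician is unblinded (SAP 9.2), so the choice among these readings should not be left open until the final results are in hand.

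**Working it through.** **1. The confidence levels do not conflict.** The upper one-sided 95% limit and the upper two-sided 90% limit both use z = 1.645.

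**2. The plan's own figure.** Inputs from Protocol 10.2 and SAP 2.5: 55% in both arms, margin 0.12, one-sided 5%, 80% power, 1:1.
- SE = sqrt(2 × 0.55 × 0.45 / n). At n = 206 per arm (412), SE = 0.0490 and power = Φ(0.12/0.0490 − 1.645) = 78.9%.
- With variance pooled over 55% and 67% (mean 0.61), power at 412 is 80.3%, and 80% needs 204.3 per arm.
- 412/0.9 = 458, consistent with 460.

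So 412 fits one unadjusted comparison. This arithmetic makes no allowance for interim looks.

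**3. Largest observed difference that passes at 460 (230 per arm).** SE = 0.0464; cut-off = 12 − 1.645 × SE in points.

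| Estimate | Cut-off (points) |
|---|---|
| Unadjusted ITT | 4.37 |
| Unadjusted PP, 90% of ITT | 3.96 |
| Unadjusted PP, 80% of ITT | 3.47 |
| Adjusted ITT, R-squared 0.1 | 4.76 |
| Adjusted ITT, R-squared 0.2 | 5.17 |

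Example: an unadjusted ITT difference of 4.2 points passes. If the adjusted ITT estimate is 5.0, the protocol's condition fails at R-squared 0.1 (5.0 > 4.76) but is met in ITT at R-squared 0.2 (5.0 < 5.17).

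**4. Joint behaviour of the limits.** Assumptions, none of them in the documents: PP is 80-95% of ITT; ITT-PP correlation is the square root of that fraction; the unadjusted estimate equals the adjusted one plus an independent covariate part; adjusted variance is (1 − R-squared) × SE², with R-squared 0-0.2. Results by simulation from this normal model, true difference zero, 460 patients:

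| Rule | Power |
|---|---|
| One unadjusted limit | 82.7% |
| Unadjusted ITT and PP | 73-79% |
| All four limits | 70-79% |
| Adjusted ITT and PP, weighting gives PP no precision gain | about 73-80% |

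A patient-level simulation (5,000 trials per setting, standardised logistic estimates for ITT, adherence weights for PP) agrees: 70.8-78.5% for all four limits and 73.4-80.2% for adjusted ITT and PP. In that simulation the weights gave PP no gain in precision. If PP equals ITT, requiring all four limits costs 0-2 points of power.

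**5. How often the rules disagree at 460 (PP 80-90%, R-squared 0.1-0.2, equal arms).**
- Unadjusted ITT and PP both pass, but the four-limit reading fails: about 2%.
- Unadjusted ITT passes, but the four-limit reading fails: about 8% (PP 90%) to 13% (PP 80%). Failure on unadjusted PP alone accounts for 5.6% and 10.2% respectively, so most of this comes from leaving PP out.

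**6. ITT adjustment method.** In a separate simulation (206 per arm, ten baseline covariates, 3,000 runs per setting), logistic and weighted ITT analyses gave different verdicts in 0.2-1.5% of runs.

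**7. False-positive rate at a true difference of 12 points, 460 patients.** One limit 5.0%; unadjusted ITT and PP 3.1-4.1%; all four 1.9-4.1%. Dilution from non-adherence is ignored.

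**The case against.** The best defence is that the documents point the same way in substance. SAP 7.2 begins with both populations and speaks of intervals in the plural, SAP 7.7 treats ITT and PP as parts of the primary analysis, and SAP 7 keeps the adjusted analyses in the decision. SAP 7 can also be read as a general statement that 7.2 details by population. On that view the disagreement is about 2% of trials, and no reading exceeds 5% type 1 error before dilution.

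Much of this stands, and it rules out several stronger readings that a reader might infer:

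- *The SAP has dropped the adjusted condition, and SAP 1 makes that binding.* Not supported: SAP 7 retains the condition, so the SAP contradicts itself.
- *Unadjusted ITT alone decides.* The wording of 7.2 and 7.7 makes this less likely, so 8-13% should not be the headline.
- *The sample size is wrong.* It is consistent with a single comparison. What is missing is a power statement for a rule with several limits.
- *The rule was loosened in the light of data.* The SAP's reference list has an access date (20 February 2023) after the end of follow-up (14 February 2023), but nothing shows that results influenced the wording.

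The defence does not remove the conflict itself. No sentence says which estimates in which populations must pass, and Protocol 10.1 prescribes weighting without the split that SAP 7.2 makes.

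**Conclusion.** The concern holds as a contradiction in the primary decision rule: between Protocol 10.1 and SAP 7.2, and between SAP 7 and SAP 7.2. It should be resolved because the main conclusion cannot be derived uniquely from the text. The practical size is modest on the likelier reading (about 2% of truly equal trials at 460) and larger only if PP has no say. Both figures rest on assumed PP fractions and covariate strength. The four-limit reading is the natural one for the protocol, but the protocol does not spell it out. The conflict over ITT adjustment is a lesser matter, although the missing step from the logistic model to a risk difference needs to be filled.

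**What to change.** Before the final comparative analysis, and with the DSMB approval that SAP 4 requires for amendments, put one rule in Protocol 10.1 and SAP 7.2. (Interim looks at the primary endpoint are planned, so a deadline before any comparative look may no longer be achievable.) By default, carry the protocol's condition into the SAP:

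> *Non-inferiority is concluded only if the upper limits of the two-sided 90% CIs for the risk difference, unadjusted and adjusted, in both the ITT and PP populations, are all below 12%.*

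If a different rule is preferred, record it as a departure from Protocol 10.1 and justify it. Then:

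- name one adjustment method for ITT, make SAP 7 and 7.2 agree, and report the result as a standardised risk difference with its CI;
- state the power of the chosen rule under a stated adherence assumption.

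The cost is wording in two documents and one approval. The stated power becomes somewhat less favourable: at 460, about 70-79% for all four limits, or 73-80% for adjusted ITT and PP, against 83% for one unadjusted limit.
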